A power analysis was conducted for the post-operative pain outcomes; being a novel intervention, opioid taper outcomes were not considered. Estimated group means, variances, and effect-size were drawn from the literature.^{41,42} The sample size estimate was derived for the primary outcome variable, chronic pain severity, using an expected baseline mean of 4.82 (Effect size: 0.33). Based on estimates obtained, a sample size of 75 participants provides 80% power to detect a pre-post improvement in pain severity (14.5%), depression (21.3%), anxiety (24.3%), and catastrophizing (29.5%), statistically significant at alpha of 0.05. Being a novel intervention, the analysis for chronic post-surgical pain will be considered exploratory and used to obtain effect size estimates. We anticipate a low attrition rate (10%) and will over-recruit 16 additional participants (total 83 subjects per group) to retain adequate power.

2. Key Inclusion Criteria:

[figure not shown]

Figure 1. Predictive factors of CPSP following TKA

1. Males and females, age > 21 years
2. Chronic non-malignant pain of at least 3 months duration
3. Morphine equivalent daily dose (MEDD) > 50 milligrams for at least 3 months
4. Able to enroll at least 4 weeks prior to planned surgery
5. Able to speak, read and comprehend in English at the 6th grade or higher proficiency

Participants will be selected so as to represent the gender, ethnicity, and age of the patient population of individuals seeking TKA in greater Philadelphia area, thus the sample is expected to be 50% women, 55% white, 35% African-American, 6-8% Latino, and 2-4% other or multiracial, and on average 67 years of age. No restrictions on gender or ethnicity will be applied. Because total knee arthroplasty surgery is uncommon in children, individuals under the age of 21 will not be included in this proposed study.

3. Key Exclusion Criteria:

1. Pain of malignant origin
2. Current or past history of opioid use disorder (including those on medication-assisted therapy)
3. Revision of TKA
4. Comorbid CNS disease such as dementia, HIV, psychosis, poorly controlled bipolar disorder or any condition interfering with informed consent

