Pain of malignant origin is likely to worsen with disease progression over time, thus the efficacy of the intervention on pain outcomes would be limited. Similarly, opioid use in patients with opioid use disorder is motivated by factors other than pain, thus opioid use outcomes would be spurious if these patients were included in the analysis. Finally, surgical outcomes for patients undergoing a revision of their TKA have poorer pain and functional outcomes, introducing known variance to the efficacy of the intervention; excluding them from the sample preserves homogeneity as required for a small pilot study.

4. Subject Recruitment and Screening:

Participants will be recruited from those preparing to undergo total knee arthroplasty (TKA) surgery at the large and nationally-renowned Department of Orthopedic Surgery at the Penn Presbyterian Medical Center. The Center performs approximately 1100 major TKAs per year with an estimated 20-30% of patients who have been taking opioids regularly for at least 3 months for the treatment of a chronic nonmalignant pain condition.

The EHR of all patients scheduled for TKA at least 5 weeks in the future will be examined to identify those meeting inclusion criteria. Eligibility will be reviewed by Co-I [name]; those eligible will be contacted by the study coordinator to inform them about the study. Those who express interest will be scheduled for a screening visit during which informed consent will be obtained in a Center private room.

If a patient assigned to standard treatment requests the enhanced treatment, he or she will be removed from the study.

5. Early Withdrawal of Subjects:

Subjects may be withdrawn from the study prior the expected completion of the project if there are concerns about the safety of the subject, failure of subject to return for visits, failure to locate the subject and if subjects withdraw their consent. Concerns about safety include feelings of extreme anxiety or depression which will be evaluated by co-PI [name].

Subjects are also informed via the informed consent process that they are free to leave the study at any time, and that withdrawal will not interfere with their future care.

6. Vulnerable Populations:

Children, pregnant women, fetuses, neonates, or prisoners are not included in this research study.

7. Populations vulnerable to undue influence or coercion:

The population from which the sample will be recruited are not vulnerable to coercion or undue influence.

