STUDY DESIGN:

A randomized clinical trial is proposed to evaluate the efficacy of the novel computer-assisted preoperative CBT/opioid sparing intervention to affect acute and chronic post-operative pain outcomes. Specifically, 150 male and female patients meeting study inclusion criteria and preparing to undergo TKA at the Penn Presbyterian Medical Center will be randomized to either receive the computer-assisted preoperative CBT intervention (n=75) or treatment-as-usual (control, n=75). The effectiveness of the intervention to address the preoperative risk factors for CPSP will be evaluated by comparing pain severity, opioid use, symptoms of depression, anxiety and pain catastrophizing before and following the 4-week pre-surgical period and compared within and across subjects. Post-operative pain severity will be abstracted from the electronic health record (EHR) and compared to post-operative pain severity ratings between the intervention and control groups. Similarly, group differences will be inspected for rates of CPSP at 3- and 6-months following surgery. In addition, due to the novelty of the CBT/opioid sparing intervention, brief (15-20min) qualitative interviews will be conducted with the participants who received it during the study visit immediately prior to surgery, to assess patient utilization, and satisfaction with the program in general, and the opioid taper component specifically; adherence is tracked by the PAINTrainer. Participants will be prompted to comment on the perceived ease of use, burden, helpfulness and quality of the CBT intervention.

A randomized clinical trial was designed because it provides the highest level of evidence and lowest risk for bias. The methods employed are predominantly quantitative, although a qualitative survey approach is used to assess subject satisfaction with the intervention. The project is designed, staffed and budgeted to be completed in 24 months. In consultation with consultants, [name] will train the study coordinator coach on delivering the opioid taper intervention during months 1-3, during which time study start-up activities will take place. Enrollment will begin month 3; at a rate of 12-13 enrollments per month, we anticipate having enrolled 166 subjects (n=150, assuming 10% attrition) by study month 15, providing adequate time for 3- and 6-month follow up, and dissemination activities.

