For the second study objective, we expect that participants, who receive a MI intervention along with a validated computer-assisted CBT intervention for chronic pain (PAINTrainer) will demonstrate a significantly greater improvement in outcome variables from baseline vs those receiving usual care. The outcome variables will include change in the severity of pre-operative chronic pain, opioid use, and psychological risk factors (depression, anxiety, catastrophizing) for CPSP in the 4 weeks prior to surgery. Specifically, a mixed model analysis will be fit to the data using the Proc Mixed procedure in SAS.^{56,57} Residual modeling will be performed to check for significant violations in the distribution and constant variance assumptions and determine if variance stabilizing or normalizing transformations should be applied. Furthermore, sensitivity analyses will be run considering dichotomous versions of the outcome variables using multiple logistic regression.

For the third study objective, we will describe the effects of the CBT intervention on 72hr post-operative pain severity, and 3- and 6-month rates of CPSP in comparison to patients who received treatment-as-usual. A mixed effects model will be fit with Treatment Group (intervention and usual care) as a between subject factor and Time (72hr, month 3 and 6) as a categorical within-subjects factor. We will include as baseline covariates any factors that differ significantly between the groups at baseline or show significant relationships with the outcome.

Potential confounders (medical comorbidities, post-operative complications) will also be considered in the analysis.

The results from the mixed model analyses will be summarized by mean (SE) change from baseline for each group at each time point. The primary hypothesis will be evaluated at the alpha = 0.05 level and all contrasts/hypotheses will be considered exploratory and results will be interpreted with caution at alpha equal to 0.05 level. The primary goal will be to obtain reliable effect size estimates to inform larger studies. In that women are more likely to develop CPSP than men,^{8,16} sex as a biological variable will be considered as a possible moderator in all analyses.

RISK/BENEFIT ASSESSMENT:

1. Risks:

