Co-principal investigator, [name], PhD, will contribute 1.44 calendar months effort to the project over the two-year project duration. She will be responsible for obtaining IRB approval, directing development of the REDCap database, and overall coordination of the efficacy testing of the intervention. Working closely with Co-I [name], she will monitor subject recruitment and enrollment efforts and verify subject eligibility. She will also oversee the day-to-day activities and performance of the Study Coordinator, and be responsible for monitoring the accuracy, quality and completeness of data collection, ensure protocol fidelity, and compliance with all regulatory and funding agencies. She will direct data analysis, and play a primary role in dissemination of findings and grant writing.

The Co-investigator, [name] will contribute 0.6 calendar months during both years of the project. He will be responsible for working closely with Study Surgeons [name] and [name] to identify and recruit potentially eligible patients for study enrollment. He will work with the Study Coordinator to establish eligibility and obtain informed consent. Importantly, he will serve as the primary liaison to the orthopedic surgeons and the surgery service to ensure effective collaboration as a means to achieve study objectives. In addition, he will assist with data interpretation and the dissemination of findings. [name] will serve the primary study clinician, managing any health-related issues experienced by study subjects during study participation.

Statistician, [name], will contribute .45 calendar months effort to the project during Year 2 only. He will serve as the study statistician, working with the REDCap derived database to the complete the analysis as outlined in the Research Plan. Specifically, he will oversee data cleaning and variable construction, run interim analysis, and complete the descriptive and multivariate analysis required to meet the study specific aims. As results become available, he will work closely with the Co-PIs to refine the analytical plan as needed and contribute to the writing of dissemination materials.

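### Controls who ask for the enhanced treatment must be removed after assignment, with no follow-up and no as-randomised analysis stated, so the between-arm estimates are open to bias of unknown size and direction

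*Combined protocol and SAP*

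**What the plan says.** The rule is in Characteristics of the Study Population, item 4 (Subject Recruitment and Screening): "If a patient assigned to standard treatment requests the enhanced treatment, he or she will be removed from the study". Although it stands under screening, it concerns patients already assigned to an arm.

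Item 5 (Early Withdrawal of Subjects) lists the general grounds: safety concerns, "failure of subject to return for visits, failure to locate the subject and if subjects withdraw their consent". These apply to both arms and are permissive. Neither item says whether a removed participant is followed further or how data already collected are used.

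Under Statistical Analysis, Objective 2 compares improvement from baseline between arms: "a mixed model analysis will be fit to the data using the Proc Mixed procedure in SAS". The Objective 3 model has treatment group "as a between subject factor and Time (72hr, month 3 and 6) as a categorical within-subjects factor". No analysis set is defined for either. The section closes its account of the models with this aim: "The primary goal will be to obtain reliable effect size estimates to inform larger studies". Study Design justifies the design thus: "A randomized clinical trial was designed because it provides the highest level of evidence and lowest risk for bias".

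The only related figure is in Target Population and Accrual: "We anticipate a low attrition rate (10%) and will over-recruit 16 additional participants (total 83 subjects per group) to retain adequate power".

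**The concern.** Randomisation makes the arms comparable only while the people compared are those who were randomised. Here controls who ask for the intervention are taken out, while their counterparts in the CBT arm, who would also have asked, stay in. Consent comes before assignment and usual care is a class that these patients attend anyway, so controls know what they are not receiving and requests are plausible.

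Those who ask may be more distressed, or more motivated. Losing controls who would have done badly flatters the control arm and understates the effect of CBT. Losing controls who would have done well overstates it. What is at stake is the effect estimate that the plan intends to hand to a larger trial. Unlike sampling error, this bias does not shrink as patients are added.

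**Working it through.** **1. Is the rule offset elsewhere in the documents?**

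- *Follow-up.* Early Withdrawal, Subject Follow-up and Study Procedures make no provision for removed participants.
- *Missing data.* Data Management says only that gaps are corrected from source documents.
- *Objective 2 model.* Proc Mixed is likelihood-based, and no text says that a removed control's data are deleted. Under missing-at-random, data already collected could be used. The model cannot supply outcomes for a control removed before the pre-operative visit, nor correct for removal driven by motivation that is not recorded.
- *Objective 3 model.* Its time levels are 72 hours, month 3 and month 6. A control removed before surgery has no value at any of them and contributes no outcome.
- *Limit of this check.* The section on resources refers to "the analysis as outlined in the Research Plan". That plan is not among these documents, so the absence is established for these documents only.

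**2. The plan's own figures.** A two-sided paired t-test at effect size 0.33, n = 75 and alpha 0.05 has 80.5% power, so the stated 80% reproduces as a within-group pre-post test. The over-recruitment implies 83 − 75 = 8 losses per arm, 8/83 = 9.6%. That allowance covers losses of every kind, with nothing separate for removed controls.

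**3. Size of the shift.** Let p be the share of controls removed for asking. Let δ be the requesters' difference from the full control-arm mean, in SDs of the analysed outcome (for Objective 2, the change from baseline). The mean of the retained controls moves by

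shift = p/(1 − p) × δ.

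Neither p nor δ is in the documents. Assume δ = 0.2 to 0.5, in either direction. With 75 per arm analysed, the standard error of the contrast is √(2/75) = 0.163 SD. With no true effect, the false-positive rate comes from a two-sided noncentral t with 148 df and noncentrality shift/SE.

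| p | p/(1 − p) | shift (SD), δ = 0.2 to 0.5 | shift/SE | false-positive rate |
|---|---|---|---|---|
| 0 | 0 | 0 | 0 | 5.0% |
| 5% | 0.0526 | 0.011 to 0.026 | 0.06 to 0.16 | 5.05% to 5.3% |
| 9.6% (8/83) | 0.1067 | 0.021 to 0.053 | 0.13 to 0.33 | 5.2% to 6.2% |
| 10% | 0.1111 | 0.022 to 0.056 | 0.14 to 0.34 | 5.2% to 6.3% |
| 20% | 0.2500 | 0.050 to 0.125 | 0.31 to 0.77 | 6.1% to 11.8% |

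The 9.6% row is what would follow if every control loss allowed for were a request. The 20% row is about twice that allowance. A simulation of 200,000 trials at p = 9.6% and δ = 0.5 gave 6.16%, against 6.21% from the formula.

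**The case against.** The strongest reply is about weight. No request rate is known and it may be zero. The contrasts are labelled exploratory, and even at the plan's full attrition allowance the false-positive rate only reaches 5.2% to 6.2%. This stands, and it is why the point is not fatal. It does not remove the point, because the stated goal is a reliable effect estimate.

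Second, a baseline-adjusted analysis absorbs part of any prognostic difference already visible at baseline. Suppose requesters are 0.5 SD worse at both times and the baseline-outcome correlation is 0.5. The residual difference is 0.5 − 0.5 × 0.5 = 0.25 SD, the residual SD is √0.75, and the false-positive rate is about 5.4% at p = 9.6% and 7.2% at p = 20%. This is fair: the table applies only if δ is read on the scale actually analysed.

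Third, the 20% row holds 75 per arm fixed, whereas removing 20% of 83 leaves about 66 controls. With 75 against 66, the upper figure is 11.4% instead of 11.8%.

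Fourth, the SD scale does not describe CPSP rates, which are binary. That is correct. The table covers continuous outcomes, and for CPSP only the mechanism carries over.

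Fifth, the plan adjusts for baseline imbalances and outcome-related covariates, and its monitoring-board reports include reasons for attrition. Adjustment deals with measured prognosis only, and reporting describes losses without recovering the outcomes.

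**Conclusion.** The concern holds. Following the rule as written breaks the randomised comparison in one arm, and nothing in these documents restores it. The direction of the bias is unknown. On the assumed δ of 0.2 to 0.5 SD, with 75 per arm analysed, the shift at the plan's whole attrition allowance is at most about a third of a standard error. It is three quarters of one only if about twice that share of controls ask. It is nil if none do. The reading of the text is secure; the size rests entirely on assumed p and δ. This should be fixed because it is avoidable at little cost, not because it sinks the trial.

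**What to change.** Replace the removal sentence with:

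> A control participant who requests or obtains the enhanced treatment stays in the study; the request and any exposure are recorded, all scheduled outcome data are collected unless consent is withdrawn, and the participant is analysed in the arm assigned.

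Add to Statistical Analysis:

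> The primary analysis includes all randomised participants as assigned. For Objective 2, baseline is a response level in the likelihood-based mixed model, so participants lacking post-baseline data are kept under missing-at-random. Removals and withdrawals are reported by arm with reasons.

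Objective 3 has no baseline level, so there the remedy is the continued follow-up itself. Whether a control who asks is given access is for the investigators to decide.

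The cost is four sentences of text. The data collection schedule already lists the outcomes for both arms, so no visit or instrument is added. Two passages need reconciling with that schedule: Study Procedures describes the pre-operative session for the experimental group only, and the follow-up text gives the BPI at 3 and 6 months only if CPSP is present.

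There are two downsides. If access is granted, the contrast is diluted in proportion to exposure: by 10% to 20% of the effect if 10% to 20% of controls received its full effect. Recording exposure lets this be examined. If access is refused, some controls may still withdraw consent, so retention is not assured.

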COVER PAGE

Pre-op Cognitive Behavior Therapy to Decrease Chronic Post-Surgical Pain in TKA

NCT04814992

November 23, 2020

PRINCIPAL INVESTIGATORS: [name] & [name], PhD, FAAN

PROTOCOL TITLE: Pre-op CBT to Reduce the Risk for Development of Chronic Post-surgical Pain in Patients undergoing Total Knee Arthroplasty

INTRODUCTION AND PURPOSE:

A significant number of patients develop chronic post-surgical pain following knee joint replacement surgery, and the risk factors for this problematic outcome have been identified. Proposed is the development and preliminary efficacy testing of a novel computer-assisted cognitive behavioral intervention integrating opioid taper delivered in the four weeks prior to surgery to address these risk factors, with the expectation that both the severity of post-operative pain and the subsequent incidence of chronic post-surgical pain will be reduced. In that chronic post-surgical pain brings with it diminished functionality and quality of life, ongoing opioid use, and direct patient costs, it is critical that interventions aimed at mitigating its development are implemented and evaluated in the clinical setting.

OBJECTIVES:

In a sample of adult men and women with chronic pain, on opioid therapy and undergoing a planned TKA, the objectives of this randomized clinical trial are to:

1. Add a motivational interviewing component to a validated computer-assisted CBT intervention for chronic pain (PAINTrainer) to encourage opioid tapering in the 4 weeks prior to surgery.
2. Describe the efficacy of the 4-week targeted pre-operative CBT intervention in 75 TKA patients to decrease preoperative chronic pain severity, preoperative opioid consumption, and symptoms of depression, anxiety and pain catastrophizing prior to surgery in comparison to 75 TKA patients randomized to treatment-as-usual.
3. Describe the effects of a 4-week targeted pre-operative CBT intervention in 75 TKA patients on 72hr post-operative pain severity, and 3- and 6-month rates of CPSP in comparison to 75 TKA patients randomized to treatment-as-usual.

BACKGROUND:

Knee Joint Replacement and Chronic Post-surgical Pain

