Pain catastrophizing – Pain catastrophizing will be measured by the Pain Catastrophizing Scale (PCS).⁵³ The PCS is a 13-item self-report scale, with each item rated on a 5-point scale: 0 (Not at all) to 4 (all the time). It is broken into three subscales (magnification, rumination, and helplessness); results from the initial development and validation studies indicate that the PCS is a reliable and valid measurement tool for catastrophizing in clinical and non-clinical populations. PCS will be completed prior to and following completion of the intervention and at the 3- and 6-month follow ups to assess the durability of the intervention.

Depression and Anxiety - To measure symptoms of depression and anxiety, the PROMIS® (Patient-Reported Outcomes Measurement Information System) person-centered measures will be utilized.⁵⁴ Specifically, the 8-item PROMIS depression and anxiety short forms will be compared prior to and following completion of the intervention; to evaluate the stability of CBT skills, the PROMIS will also be administered at 3 and 6 months.

Potential confounders – Pre-existing medical comorbidities or post-operative complications may affect surgical outcomes with respect to pain severity and resolution. To account for the effects of these confounders, all medical comorbidities will be extracted from the EHR by the study coordinator prior to surgery and recorded in the study database. Also added to the study database will be any unanticipated adverse events following surgery, and with medical comorbidities, considered as moderators of the effects of the intervention on the development of CPSP.

Post-operative pain intensity – Severity of post-operative pain will be operationalized as (1) responses on a visual analogue pain scale (VAS) and (2) consumption of opioid analgesic medications during the first 72 hours following surgery. The VAS ranges from 0 (no pain) to 10 (worst pain imaginable), and pain scores are collected every 4 hours as part of routine practice. Pain ratings will be graphed over time and area under the curve calculated. Dose of opioid analgesics consumed during this period (24hr increments and total) will be abstracted from the electronic health record and converted into MEDD for analysis.

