Opioid taper: As a part of the intervention and with the guidance of their trained coach, one-half of the subjects will be encouraged to gradually taper their opioid use in the month prior to surgery. It is possible that in doing so, subjects may experience the uncomfortable symptoms associated with opioid withdrawal. To avoid the emergence of these, subjects will be instructed to taper their dose gradually (no more than 10%/week), and will be provided with information on how to self-manage these symptoms should they arise. In addition, subjects will be instructed to contact their coach should the symptoms become severe, to receive guidance on how to temporarily cease and then restart taper attempts. In that subjects will have been regular users of opioids for at least three months prior to study enrollment, they will have developed a certain degree of physiologic tolerance, offering protection against any respiratory depressant effects during a taper pause.

Breach of Confidentiality: Participation in this study may constitute a social risk to the participant in that others may learn that he or she has chronic pain and is taking opioid medications. Due to the sensitive nature of this information, privacy and confidentiality will be strictly maintained in all aspects of participation. Consent and data collection sessions will take place in private rooms where strict privacy is enforced and all staff are HIPAA certified.

Acute Anxiety or Depressive Symptoms: It is possible that the opioid taper for the intervention group, or the upcoming surgery for both groups may precipitate unanticipated symptoms of acute anxiety or depression. As described below, co-PI [name] is a licensed clinical psychologist with over 40 years' experience in treating patients with chronic pain, will be available to assess and intervene with patients who experience these distressing symptoms during the pre-operative period.

2. Benefits:

The potential benefit for both the participants and broader segments of society is to improve pain outcomes following a very common procedure, TKA, ideally decreasing the severity of post-operative pain experienced and

the development of CPSP. Development of an effective intervention to address the risk factors for poor pain outcomes following TKA can guide clinical practice based upon evidence.

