The Study Coordinator/Coach, TBH, will devote 12 calendar months effort to the study over both years of the project. This individual will come to the project with experience in coordinating human subject clinical research studies and be responsible for enrolling subjects, scheduling study visits, all aspects of data collection, entering study data into REDCap, and engaging in ongoing communication with IRB, study setting and U Penn School of Medicine and Nursing, Department of Anesthesiology and Department of Orthopaedic Surgery. In addition, this individual will receive directed training and monitoring from Co-PI [name] to oversee delivery of the CBT and opioid tapering MI intervention. In this role, this individual will serve as a "coach" to the subjects, contacting them on a weekly basis prior to surgery, educating and motivating them to engage in preoperative opioid reduction.

Participants will be recruited from the nationally renowned Department of Orthopaedic Surgery at PPMC. Center surgeons perform approximately 1800 major TKAs per year, an estimated 20-30% of whom have been taking opioids for at least 3 months for the treatment of a chronic nonmalignant pain condition, resulting in a recruitment pool of 30 to 45 patients per month, providing an adequate source of the necessary 12-13 enrollments per month.

In addition, the facilities and resources are adequate to safely conduct the study. Situated within the Department of Psychiatry is the Center for Studies on Addiction (CSA), where Co-Principal Investigator [name] holds an appointment. A primary mission of the CSA is to continue to advance the cutting edge of knowledge on the nature of addiction and the best ways to treat this disorder. The CSA has, for the past 40 years, been an important

national and international resource for addictions research. The PI ([name]) has conducted large-scale studies on pain and opioid use disorders and suicide and has an established relationship at the primary recruitment site.

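### Patients may be withdrawn from the study for extreme anxiety or depression, with no provision to collect their outcomes afterwards, so Objective 2 mood scores can be lost for reasons related to mood

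*Combined protocol and SAP*

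**What the plan says.** The rule is in section 5, Early Withdrawal of Subjects, under Characteristics of the Study Population: "Subjects may be withdrawn from the study prior the expected completion of the project if there are concerns about the safety of the subject". The scope is the study, not only the taper or the coaching. The section continues: "Concerns about safety include feelings of extreme anxiety or depression", to be evaluated by a co-principal investigator. A further listed reason is "failure of subject to return for visits".

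Objective 2 covers pre-operative pain severity, opioid consumption and "symptoms of depression, anxiety and pain catastrophizing prior to surgery". Under Study Instruments, "the 8-item PROMIS depression and anxiety short forms will be compared prior to and following completion of the intervention". The Statistical Analysis section names as outcomes the "psychological risk factors (depression, anxiety, catastrophizing) for CPSP in the 4 weeks prior to surgery" and fits a mixed model.

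On the arms, the Risks section says: "It is possible that the opioid taper for the intervention group, or the upcoming surgery for both groups may precipitate unanticipated symptoms". The resources section describes the coach's work with subjects as "contacting them on a weekly basis prior to surgery, educating and motivating them to engage in preoperative opioid reduction". Between baseline and the pre-operative visit (T0), the control arm has the standard education class and no scheduled study contact.

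On missing data, the Data Management section provides only for correction from source documents. No section continues outcome collection after withdrawal or defines an analysis set of all randomized patients.

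**The concern.** A high level of anxiety or depression can lead to withdrawal before that anxiety or depression is measured at T0. The missing score is then probably a high one. If this happens equally in both arms, the comparison between arms is little affected. If it happens more in one arm, that arm's mean distress looks too low.

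The plan gives two reasons to expect more of it in the intervention arm: the taper is a possible cause of distress there only, and weekly coaching gives more chances to notice it. Fewer high scores in that arm would make the intervention look better for mood than it is.

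The mixed model does not fully correct this. It allows for loss that recorded values explain, but distress told to a coach between visits is not a recorded PROMIS score. This matters because the Statistical Analysis section makes reliable effect size estimates for larger studies the primary goal.

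**Working it through.** **Inputs from the plan.** Planned size is 75 per arm, raised to 83 for 10% attrition; alpha is 0.05 (sidedness not stated, two-sided assumed); effect size is 0.33 for pain severity.

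**The plan's own figures.** A paired t-test with effect size 0.33 and two-sided alpha 0.05 needs n = 75 (power 80.5%), so 75 reproduces as a within-group pre-post figure. For attrition, 75 × 1.10 = 82.5, rounded up to 83 (75 / 0.90 gives 84). Because 0.33 reproduces as a paired pain effect, it is not a yardstick for a between-arm shift in mood.

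**Assumptions.** The plan gives no withdrawal rates by arm, PROMIS SD or baseline to T0 correlation r. Assumed: no true effect, normal scores, 83 per arm, r of 0.5 or 0.7. Two loss rules were used: the highest T0 distress scores are lost (strict), or the highest values of score plus equal-variance noise are lost (loose). There were 4000 simulated trials per setting.

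**Closed-form check, strict rule.** Losing the top fraction p lowers the raw mean by δ = φ(z) / (1 − p). For p = 0.05, δ = 0.1031 / 0.95 = 0.109 SD; for p = 0.10, δ = 0.1755 / 0.90 = 0.195 SD. The baseline mean of those remaining falls by rδ, so adjusting for baseline with slope r leaves δ − r × rδ = δ(1 − r²):

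- p = 0.05: 0.109 × 0.75 = 0.082 (r = 0.5); 0.109 × 0.51 = 0.056 (r = 0.7)
- p = 0.10: 0.195 × 0.75 = 0.146 (r = 0.5); 0.195 × 0.51 = 0.099 (r = 0.7)

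The simulated values, for 4 and 8 lost of 83, are 0.078 and 0.054, and 0.145 and 0.103. The two agree.

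**Simulation results.** Ranges cover both rules and both correlations. Bias is from the baseline-adjusted and mixed-model estimates and favours the intervention.

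| Lost, intervention vs control | Bias (SD) | Type I error |
|---|---|---|
| 0 vs 0 | about 0 | 4.3% to 5.2% |
| 4 vs 4 | about 0 | 5.0% to 6.7% |
| 2 vs 0 | 0.02 to 0.04 | 5.6% to 6.9% |
| 4 vs 0 | 0.04 to 0.08 | 6.6% to 9.4% |
| 8 vs 4 | 0.03 to 0.07 | 6.8% to 10.7% |
| 8 vs 0 | 0.07 to 0.145 | 9.6% to 20.8% |

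A simple comparison of change scores among completers gives less: 0.025 to 0.051 SD at 4 vs 0 and 0.039 to 0.095 SD at 8 vs 0. The bias comes from the difference in loss between arms. With the arms exchanged, the sign reverses.

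**Chronic post-surgical pain (CPSP).** Assume a 50% rate (Background: 44% to 53%) and 3.4-fold odds in those lost, the figure that the Background gives for pre-operative distress. If 5% of one arm is lost, a rate of 0.486 in the rest means odds of 0.946; 0.946 × 3.4 = 3.21, a rate of 0.763 in those lost; and 0.05 × 0.763 + 0.95 × 0.486 = 0.50. The observed rate falls by 0.500 − 0.486, or 1.4 points. At 10% lost, the same steps give about 3 points. The standard error of the difference at 80 per arm is √(2 × 0.25 / 80) = 0.079, or about 8 points.

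**The case against.** Much can be said for the plan as written, and several stronger readings fail.

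- **That the withdrawal criterion is the endpoint itself.** A reader might infer this. However, the endpoint is a PROMIS score at scheduled visits, whereas the trigger is clinically evaluated distress with no score cut-off. Withdrawal is discretionary, and the Data and Safety Monitoring section answers a high depression score with assessment and a treatment plan. A score already recorded at T0 is not said to be deleted. For mood in Objective 2, the exposure is therefore loss between baseline and T0.
- **That the mood results will favour the intervention.** The plan does not establish this. Surgery is a trigger in both arms, and referral for assessment covers any patient. The recruitment section also removes controls who request the enhanced treatment. If these tend to be the more distressed controls, the bias runs the other way.
- **That the shift is 0.11 or 0.195 SD, a third or more of the planned effect.** Those are raw-mean shifts that ignore baseline, and the ratio sets mood against a paired pain effect size.
- **That catastrophizing and CPSP are distorted to the same degree.** Catastrophizing is not a withdrawal trigger and is affected only through its correlation with distress. The CPSP shift is small beside its standard error, and the plan calls that analysis exploratory.
- **That harm from the taper is hidden.** The monitoring board receives reasons for attrition and all adverse events with severity and relatedness. What can be lost is harm in the efficacy comparison.

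The missed-visit reason is the weaker part. The main visit to return for is T0, immediately before surgery, and a patient absent then may not have had surgery. No section links absence to distress. Still, if surgery goes ahead, the 72-hour data come mainly from the health record and later outcomes by telephone, so a missed T0 session alone need not cost them.

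What stands is that withdrawal is from the study, that distress is a named ground, and that nothing provides for outcomes afterwards.

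**Conclusion.** The concern holds as a risk of bias in the anxiety and depression comparisons at T0. Following the stated rule can remove outcome data for a reason related to the outcome, and the mixed model does not fully repair it. Unequal loss is plausible from the taper and the weekly coaching, but it is inferred, and the net direction is not settled.

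Under the stated assumptions, the bias is about 0.04 to 0.08 SD at 4 versus 0 lost (type I error about 7% to 9%), about 0.07 to 0.145 SD at 8 versus 0 (about 10% to 21%), and about zero with equal loss. The 8 versus 0 case is an outer one, since it puts one arm's whole planned attrition into highly distressed patients. Effects on catastrophizing and CPSP are indirect and smaller. The plan should be changed, because the remedy is cheap and the trial's aim is reliable effect sizes.

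**What to change.** Leave the clinical and safety decisions in the Early Withdrawal, Risks and Data and Safety Monitoring sections as they are. Change only data collection and analysis:

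- State in Early Withdrawal of Subjects that stopping the intervention, or being withdrawn for safety or a missed visit, does not by itself end outcome collection.
- Unless the patient withdraws consent to data collection, or the evaluating clinician judges further contact inappropriate, seek the PROMIS and other T0 measures, the 72-hour health record data and the 3- and 6-month telephone outcomes.
- Record a missed visit as a missed visit.
- In Statistical Analysis, analyse all randomized patients in their assigned arm, and report withdrawals by arm and reason.

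If the T0 scores are obtained, the selective loss disappears: the simulation then shows bias of about zero and type I error of about 5% (4.3% to 5.2%). The cost is protocol and consent wording and a few extra telephone contacts. The mood results may also look less favourable.
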